12.1 Criteria for response

The main endpoint in this study is the ORR of ADV/HSV-tk + Valacyclovir therapy in combination with SBRT used as a window of opportunity treatment before nivolumab in patients with metastatic squamous or non-squamous NSCLC and metastatic uveal melanoma. RECIST criteria 1.1 will be used to select patients with detectable or measurable disease as part of the initial inclusion process. Modified irRC and RECIST 1.1 will be used to assess treatment response.

12.2 RECIST

RECIST offers a simplified, conservative, extraction of imaging data for wide application in clinical trials. They presume that linear measures are an adequate substitute for two-dimensional methods and register four response categories.¹⁹⁰

Target Lesions (Main Tumor)

- **Complete Response (CR):** Disappearance of all target lesions. Any pathological lymph nodes (whether target or non-target) must have reduction in short axis to <10 mm.
- **Partial Response (PR):** At least a 30% decrease in the sum of the diameters of target lesions, using the baseline sum diameters as the reference.
- **Progressive Disease (PD):** At least a 20% increase in the sum of the diameters of target lesions, using the smallest sum on study (includes the baseline sum) as the reference. In addition to the relative 20% increase, the sum must also demonstrate an absolute increase of at least 5 mm. (Note: the appearance of one or more new lesions is also considered progression)
- **Stable Disease (SD):** Neither sufficient shrinkage to qualify for PR nor sufficient increase to qualify for PD, using the smallest sum diameters while on study as the reference.

Non-Target Lesions (Lymph Nodes)

- **CR:** Disappearance of all non-target lesions and normalization of tumor marker levels. All lymph nodes must be non-pathological in size (<10 mm short axis).

Note: If tumor markers are initially above the upper normal limit, they must normalize for a patient to be considered in complete clinical response.

- Non-CR/Non-PD: Persistence of one or more non-target lesion(s) and/or maintenance of tumor marker levels above the normal limits.
- PPD: Appearance of one or more new lesions and/or *unequivocal progression* of existing non-target lesions. *Unequivocal progression* should not normally trump target lesion status. It must be representative of overall disease status change, not a single lesion increase.
- Although a clear progression of “non-target” lesions only is exceptional, the opinion of the treating physician should prevail in such circumstances, and the progression status should be confirmed at a later time by the review panel (or principal investigator).

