1.1 Overview of disease pathogenesis, epidemiology, and current treatment

Lung cancer is the leading cause of cancer death in the United States. Lung and bronchial cancer are expected to account for an estimated 221,200 new cases (115,610 in men and 105,590 in women) and 158,040 deaths (86,630 in men and 71,660 in women) in 2015.¹ Only 16.8% of lung cancer patients are alive for 5 years or more after their diagnosis. Non-small cell lung carcinoma (NSCLC) accounts for over 85% of all lung cancer cases. Most patients are diagnosed with advanced or metastatic (stage IIIB/IV) disease,² and current first-line treatment options for these patients are limited. In patients with advanced NSCLC, first-line platinum-based doublet chemotherapy yields 1-year overall survival (OS) rates of only 30–40% and can cause significant toxicities that may complicate treatment.² However, much progress has recently been made in the diagnosis and treatment of lung cancer including screening methods, minimally invasive techniques for diagnosis and treatment, and advances in radiation therapy (RT), including stereotactic body RT (SBRT), targeted therapies, and immunotherapies.^{3–6}

Uveal melanoma represents approximately 85% of all ocular melanomas. Metastatic disease develops in up to 50% of patients and is associated with poor prognosis.⁷ The most frequent site of metastasis is the liver (95%), followed by the lungs (24%), bone (16%), and skin (11%).^{8,9} Median survival for patients with liver metastases is approximately 4–6 months with a 1-year survival of approximately 10–15%, whereas patients with metastases not involving the liver have a median survival of approximately 19–28 months with a 1-year survival of approximately 76%.^{10–12} There is no proven treatment for metastatic uveal melanoma, and standard therapies for cutaneous melanoma are often adopted but show limited activity.¹¹ As uveal and cutaneous melanomas exhibit marked differences in their molecular features,¹³ dedicated therapies for metastatic uveal melanoma are needed to improve the outcomes of patients with this hard-to-treat disease.

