12.3 Modified irRC, derived from RECIST 1.1¹⁹¹

This new classification is based on recent clinical studies showing delays in tumor regression or stabilization with cancer immunotherapies. For the ENSIGN trial, the concepts of the irRC are combined with RECIST 1.1 to come up with the modified irRC, which uses unidimensional measurements. For modified irRC, only target and measurable lesions are taken into account. In contrast to RECIST 1.1, the modified irRC criteria (a) require confirmation of both progression and response by imaging at eight 8 weeks after initial imaging (evidence of cancer progression within the first 3 months on bone scan only should be interpreted with extreme caution due to risk of tumor flare) and (b) do not necessarily score the appearance of new lesions as PD if the sum of the diameters of target lesions (minimum of 10 mm per lesion, maximum of 5 target lesions, maximum of 2 per organ) and measurable new lesions does not increase by $\geq 20\%$. The same assessment method and technique should be used to characterize each identified and reported target lesion(s) at baseline, during the trial, and at EOT. All measurements should be recorded in metric notation. The modified irRC based on RECIST 1.1 are displayed below. Modified irRC are defined as follows:

- New measurable lesions: Incorporated into tumor burden.
- New non-measurable lesions: Do not define progression but preclude irCR.
- Overall irCR: Complete disappearance of all lesions (whether measurable or not) and no new lesions. All measurable lymph nodes also must have a reduction in short axis to 10 mm or less.
- Overall irPR: $\geq 30\%$ decrease in the sum of the longest diameters of target and new measurable lesions.
- Overall irSD: Neither sufficient shrinkage to qualify for irCR or irPR (compared to baseline) nor sufficient increase to qualify for irPD (compared to nadir), using the sum of the longest diameters of target and new measurable lesions.
- Overall irPD: $\geq 20\%$ increase in the sum of the longest diameters of target and new measurable lesions increases (compared to nadir), confirmed by a repeat, consecutive observation at least 6 weeks (normally it should be done at 8 weeks) from the date first documented.

Documentation of immune-related PD (based on modified irRC) does not mandate discontinuation of the study treatment even after irPD is confirmed with CT scan 6 weeks after the initial observation of irPD.

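### Section 12.2 labels RECIST target lesions as the main tumor and non-target lesions as lymph nodes; this contradicts its own rules and, read literally, leaves other existing organ metastases unscored in the primary ORR.

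*Combined protocol and SAP*

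**What the plan says.** Sections 4 and 12.1 name RECIST 1.1 and modified irRC as the criteria for treatment response, and ORR is the primary endpoint.

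Section 12.2 sets out the RECIST rule in two parts, headed "Target Lesions (Main Tumor") and "Non-Target Lesions (Lymph Nodes"). It states no number of target lesions, no limit per organ and no minimum size, and it does not say that all remaining lesions are non-target.

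The rules under those headings read more widely:
- Partial response is "At least a 30% decrease in the sum of the diameters of target lesions, using the baseline sum diameters as the reference".
- On nodes: "Any pathological lymph nodes (whether target or non-target) must have reduction in short axis to <10 mm".
- Non-target progression is "Appearance of one or more new lesions and/or" unequivocal progression of existing non-target lesions.
- A note to the target rule adds that "the appearance of one or more new lesions is also considered progression".

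Section 12.3 (modified irRC) does give a selection rule: "minimum of 10 mm per lesion, maximum of 5 target lesions, maximum of 2 per organ". Section 8.1 uses target lesion for the lesion that will receive SBRT, and non-target lesion for a lesion of at least 1 cm used to judge the abscopal effect, with no restriction to nodes.

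**The concern.** Both cohorts have metastatic disease. For metastatic uveal melanoma, Section 1.1 puts the liver at 95% of cases, lung at 24%, bone at 16% and skin at 11%. If the labels are followed, only the main tumor enters the target sum and only nodes are assessed as non-target. A second liver or lung metastasis already present at baseline has no place. New lesions are still caught, so the gap concerns existing ones.

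The main tumor could well be the locally treated lesion, because Section 9.3 directs SBRT to the largest tumor when there are several. The labels could then give weight to local control when the hypothesis in Section 3 is about systemic response. At stake are the RECIST version of the primary ORR and the progression calls behind PFS, DoR and, if it counts stable disease (the plan does not say), CBR.

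**Working it through.** **Step 1. Labels against the other text.**

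| Source | What it implies |
|---|---|
| 12.2 headings | Target = main tumor; non-target = lymph nodes |
| 12.2, target rules | A sum of diameters over lesions in the plural |
| 12.2, node rule | A node may be target or non-target |
| 12.2, non-target CR | All non-target lesions gone, and separately all nodes of normal size, so non-target is wider than nodes |
| 8.1 | A non-target lesion is any lesion of at least 1 cm |
| 12.3 | Up to 5 target lesions, 2 per organ, at least 10 mm |

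The labels stand alone against the rest, but nothing in the plan withdraws them.

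**Step 2. What the labels can do to a call.** The sizes are assumed: one lung mass as main tumor, two liver metastases of 20 mm each at baseline, nodes stable, no new lesions. All three lesions fit the 12.3 limits. Change = (follow-up sum - baseline sum) / baseline sum.

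| Case | Lung (mm) | Liver sum (mm) | By the labels | All lesions |
|---|---|---|---|---|
| A | 50 to 30 | 40 to 60 | -20/50 = -40%, PR | 90 to 90, 0%, SD |
| B | 50 to 45 | 40 to 10 | -5/50 = -10%, SD | 90 to 55, -35/90 = -39%, PR |
| C | 50 to 45 | 40 to 70 | -10%, SD | 90 to 115, +25/90 = +28% and +25 mm, PD |

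A adds a false responder and B loses a true one. C leaves ORR unchanged but moves the progression date (baseline is taken as the smallest sum).

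**Step 3. The plan's own test.** Section 15.1 gives N = 16 with ORR 3% against 25% (power 80.3%), and N = 9 with 3% against 30% (power 80.4%), both one-sided at 0.05. The exact binomial tail is P(X >= r | n, p) = 1 - sum over k < r of C(n,k) p^k (1-p)^(n-k).

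- NSCLC, r = 3: 1 - 0.61425 - 0.30396 - 0.07051 = 0.0113 at 3%. With r = 2 it is 0.0818, so 3 is the smallest valid cut-off. Power at 25% is 0.803.
- Uveal melanoma, r = 2: 1 - 0.7602 - 0.2116 = 0.0282 at 3%. With r = 1 it is 0.2398, so 2 is the smallest valid cut-off. Power at 30% is 0.804.

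Both stated powers are reproduced. Success therefore means 3 of 16 or 2 of 9, and one miscall changes the result at 2 of 16 or 1 of 9.

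**Step 4. Sensitivity to miscalls.** The documents give no miscall rate, so the scored ORR is an assumption throughout.

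| True ORR | Scored ORR | P(success), NSCLC | P(success), uveal melanoma |
|---|---|---|---|
| 3% | 3% | 0.011 | 0.028 |
| 3% | 5% | 0.043 | 0.071 |
| 3% | 8% | 0.131 | 0.158 |
| 3% | 10% | 0.211 | 0.225 |
| 25% / 30% | 25% / 30% | 0.803 | 0.804 |
| 25% / 30% | 20% | 0.648 | 0.564 |

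The last row shows the opposite error, in which true responses are missed.

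**The case against.** The best answer is that nobody trained in RECIST would follow the labels. The plan names RECIST 1.1, the rules in 12.2 only make sense for several target lesions, non-target progression must reflect the disease as a whole, and CT covers thorax, abdomen and pelvis. This largely stands. It makes mis-scoring less likely, but it does not remove a written rule that says something else.

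A reader might infer more than the text supports:

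- *That organ metastases will go unscored.* The body of 12.2 points the other way, so this is a contradiction and not proof of mis-scoring.
- *That ORR is biased upward, with a false-positive rate of 0.13 or 0.16.* Those values assume a 3% ORR scored as 8%, a rate with no source. Case B shows that the same labels can lower ORR.
- *That the RECIST and irRC response rates must rest on different lesion sets.* Section 12.3 derives its criteria from RECIST 1.1 and lists as departures the confirmation rule and the handling of new lesions. Target selection is not listed, so a shared set is a fair reading. Only the labels create the difference.
- *That nothing measurable counts as the main tumor in the uveal cohort.* The main tumor need not be the ocular primary. A liver metastasis, for example the largest lesion, could be the main tumor and would be measured. The gap concerns the other metastases.

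**Conclusion.** The point holds as an internal contradiction in the rule for one of the two primary-endpoint criteria. Section 12.2 carries labels that its own rules, RECIST 1.1 and Section 8.1 contradict, and no text settles which governs. If the labels are followed, existing organ metastases other than the main tumor drop out, and calls for ORR, PFS, DoR and possibly CBR can be wrong in either direction.

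The size cannot be fixed from the documents. The lesion sizes and scored rates above are illustrations. What is firm is the small margin: with cut-offs of 3 of 16 and 2 of 9, a single miscalled patient can decide a cohort. The correction should be made before responses are read.

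**What to change.** 1. In Section 12.2, delete the two parenthetical labels from the headings.
2. State there that RECIST 1.1 uses the same baseline target set as Section 12.3 (up to 5 lesions, at most 2 per organ, at least 10 mm each, organ metastases included), and that all remaining lesions at any site are non-target.
3. In Section 8.1, use another term for the lesion chosen for SBRT, so that target lesion has one meaning throughout. It would help to say at the same place whether the irradiated lesion enters the target sum.

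The cost is wording only. The same CT scans are used and no treatment rule changes. The RECIST ORR may shift slightly, in either direction, compared with scoring by the labels.

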12.3 Modified irRC, derived from RECIST 1.1¹⁹¹

This new classification is based on recent clinical studies showing delays in tumor regression or stabilization with cancer immunotherapies. For the ENSIGN trial, the concepts of the irRC are combined with RECIST 1.1 to come up with the modified irRC, which uses unidimensional measurements. For modified irRC, only target and measurable lesions are taken into account. In contrast to RECIST 1.1, the modified irRC criteria (a) require confirmation of both progression and response by imaging at eight 8 weeks after initial imaging (evidence of cancer progression within the first 3 months on bone scan only should be interpreted with extreme caution due to risk of tumor flare) and (b) do not necessarily score the appearance of new lesions as PD if the sum of the diameters of target lesions (minimum of 10 mm per lesion, maximum of 5 target lesions, maximum of 2 per organ) and measurable new lesions does not increase by $\geq 20\%$. The same assessment method and technique should be used to characterize each identified and reported target lesion(s) at baseline, during the trial, and at EOT. All measurements should be recorded in metric notation. The modified irRC based on RECIST 1.1 are displayed below. Modified irRC are defined as follows:

- New measurable lesions: Incorporated into tumor burden.
- New non-measurable lesions: Do not define progression but preclude irCR.
- Overall irCR: Complete disappearance of all lesions (whether measurable or not) and no new lesions. All measurable lymph nodes also must have a reduction in short axis to 10 mm or less.
- Overall irPR: $\geq 30\%$ decrease in the sum of the longest diameters of target and new measurable lesions.
- Overall irSD: Neither sufficient shrinkage to qualify for irCR or irPR (compared to baseline) nor sufficient increase to qualify for irPD (compared to nadir), using the sum of the longest diameters of target and new measurable lesions.
- Overall irPD: $\geq 20\%$ increase in the sum of the longest diameters of target and new measurable lesions increases (compared to nadir), confirmed by a repeat, consecutive observation at least 6 weeks (normally it should be done at 8 weeks) from the date first documented.

Documentation of immune-related PD (based on modified irRC) does not mandate discontinuation of the study treatment even after irPD is confirmed with CT scan 6 weeks after the initial observation of irPD.

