The number of immunotherapy clinical trials has dramatically increased in the past decade. These trials have shown the promise of immunotherapy in enhancing antitumor immune responses. Several clinical studies have expanded the list of cancers that can be treated with checkpoint blockade therapy. Brahmer et al. demonstrated that, among patients with previously treated advanced squamous-cell NSCLC, OS, response, and progression-free survival (PFS) rates were significantly better with the PD-1 inhibitor nivolumab than with docetaxel regardless of PD-L1 expression level.²¹ The confirmed objective response rate (ORR) was significantly higher with nivolumab than with docetaxel (20% [95% confidence interval [CI]: 14–28] vs. 9% [95% CI: 5–15]; $P = 0.008$)²¹. Herbst et al. found that treatment with MPDL3280A, a PD-L1-specific monoclonal antibody, induces therapeutic responses in patients with advanced NSCLC, renal cell cancer, and melanoma.²² Powles et al. showed that the same antibody can be used to treat urothelial bladder cancer.²³ Among patients with a minimum of 6 weeks of follow-up, ORRs were 43% (13/30; 95% CI: 26–63) for those with tumor PD-L1 immunohistochemical expression scores of 2 or 3 (2/3) and 11% (4/35; 95% CI: 4–26) for those with tumor PD-L1 immunohistochemical expression scores of 0 or 1 (0/1). In the tumor PD-L1 immunohistochemical expression 2/3 score group, the ORR included a 7% complete response rate (2/30). Among patients with a tumor PD-L1 immunohistochemical expression score of 2/3 and a minimum of 12 weeks of follow-up, an ORR of 52% (13/25; 95% CI: 32–70) was achieved. Sixteen of the 17 responders had ongoing responses, and all 17 responders continued on MPDL3280A treatment until the data cutoff date. One patient who initially responded at the first response assessment later presented with new lesions,

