Nivolumab has demonstrated efficacy in the treatment of metastatic squamous and non-squamous NSCLC. In the phase III CheckMate-017 trial, 272 patients with metastatic squamous NSCLC who had progressed during or after one prior platinum doublet-based chemotherapy regimen were randomized (1:1) to receive nivolumab (n=135; 3 mg/kg intravenous [IV] every 2 weeks) or docetaxel (n=137; 75 mg/m² IV every 3 weeks) in an open label study.³³ This study included patients regardless of their PD-1 status. Patients with autoimmune disease, symptomatic interstitial lung disease, or untreated brain metastasis were excluded. Patients with treated brain metastases were eligible if their neurological status had returned to baseline at least 2 weeks prior to enrollment and they were either off corticosteroids or on a stable or decreasing dose of <10 mg daily prednisone equivalents. Tumor assessments were conducted 9 weeks after randomization and every 6 weeks thereafter. The major efficacy outcome measure was OS. The median OS was 9.2 months (range: 7.3–13.3 months) and 6.0 months (range: 5.1–7.3 months) for nivolumab and docetaxel, respectively (P = 0.00025). The median patient age was 63 years (range: 39–85 years); 44% and 11% of patients were ≥ 65 and ≥ 75 years of age, respectively. The majority of patients were white (93%) and male (76%). Baseline Eastern Cooperative Oncology Group (ECOG) performance status was 0 in 24% of patients and 1 in 76% of patients. This trial demonstrated a statistically significant improvement in OS with nivolumab as compared with docetaxel at the prespecified interim analysis conducted when 199 events were observed (86% of the planned number of events for the final analysis). A single-arm, multinational, multicenter trial of nivolumab was conducted in patients with metastatic squamous NSCLC whose disease had progressed after receiving a platinum-based therapy and at least one additional systemic treatment regimen.²⁶ This study included patients regardless of their PD-1 status. Nivolumab (3 mg/kg) was administered intravenously over 60 minutes every 2 weeks. Patients with autoimmune disease, symptomatic interstitial lung disease, or untreated brain metastasis were excluded. Patients with treated brain metastases were eligible if their neurological status had returned to baseline at least 2 weeks prior to enrollment and they were either off corticosteroids or on a stable or decreasing dose of <10 mg daily prednisone equivalents. Tumor assessments were conducted 8 weeks after treatment start and every 6 weeks thereafter. The major efficacy outcome measure was confirmed ORR as measured by an independent review committee (IRC) using the Response Evaluation Criteria in Solid Tumors version 1.1 (RECIST 1.1). Additional outcome measures included DOR. A total of 117 patients received treatment with nivolumab. The median age was 65 years (range: 37–87 years); 50% of patients were ≥ 65 years of age and 14% of patients were ≥ 75 years of age. The majority of patients were male (73%) and white (85%). All patients received two or more prior systemic treatments; 35% received two, 44% received three, and 21% received four or more. At baseline, 6%, 94%, and 1.7% of patients had recurrent stage IIIb disease, stage IV disease, and brain metastases, respectively. Baseline ECOG performance status was 0 in 22% of patients and 1 in 78% of patients. Based on IRC review and with a minimum follow-up of at least 10 months on all patients, the confirmed ORR was 15% (17/117; 95% CI: 9–22), of which all were partial responses. The median time to onset of response was 3.3 months (range: 1.7–8.8 months). Thirteen of the 17 patients (76%) with a confirmed response had ongoing responses with durations ranging from 1.9+ to 11.5+ months; 10 of these 17 (59%) patients had durable responses of 6 months or longer.

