Nivolumab has demonstrated significant single-agent activity in metastatic melanoma. Results from CheckMate 066 (NCT01721772)³⁵ and CheckMate 067 (NCT01844505)³⁶ led to the approval of nivolumab for the first-line treatment of *BRAF* V600 wild-type and mutation-positive unresectable or metastatic melanoma. The majority of subjects in these trials had cutaneous melanoma; subjects with uveal melanoma were excluded. In a small case series of 8 patients with metastatic uveal melanoma, anti-PD-1 therapy produced objective tumor responses (CR, $n = 1$; PR, $n = 2$; stable disease, $n = 1$), suggesting its potential as a therapeutic option in this patient population.³⁷ In an analysis of 56 patients with metastatic uveal melanoma who received anti-PD-1/PD-L1 antibodies (pembrolizumab, 38 [68%]; nivolumab, 16 [29%]; atezolizumab, 2 [4%]), durable objective responses (PRs) and stable disease \geq 6 months were observed in 2 (3.6%) and 5 (9%) patients, respectively.³⁸ Median PFS (2.6 months) and OS (7.7 months) were also modestly improved. Further studies are needed to clarify the role of anti-PD-1 therapy in the treatment of metastatic uveal melanoma. Several ongoing clinical trials are investigating the use of nivolumab in combination with ipilimumab in this patient population: Phase II Multicenter, Non-Randomized, Open-Label Trial of Nivolumab in Combination with Ipilimumab in Subjects with Previously Untreated Metastatic Uveal Melanoma (NCT02626962) and Phase II Study of Nivolumab in Combination with Ipilimumab for Uveal Melanoma (NCT01585194).

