14.3 Pregnancy

To ensure patient safety, each pregnancy occurring while the patient is on study treatment must be reported to the local IRB within 24 hours of learning of its occurrence. The pregnancy should be followed up to determine outcome, including spontaneous or voluntary termination, details of the birth, and the presence or absence of

any birth defects, congenital abnormalities, or maternal and/or newborn complications. The newborn will be followed for at least 12 months.

Pregnancy should be recorded on a Clinical Trial Pregnancy Form and reported by the investigator to the local IRB. Pregnancy follow-up should be recorded on the same form and should include an assessment of the possible relationship to the study treatment and any pregnancy outcome. Any SAE experienced during pregnancy must be reported on the SAE Report Form.

15 Statistical methods

15.1 Sample size.

Study Design and Sample Size Calculation: For the NSCLC cohort, a sample size of 16 patients achieves 80.3% power to detect the difference between a null hypothesis of ORR of 3% and treatment ORR of 25% (alternative hypothesis) at a 0.05 significance level (i.e., alpha) in a one-sided Fisher's exact test. For the uveal melanoma cohort, a sample size of 9 patients achieves 80.4% power to detect the difference between a null hypothesis of ORR of 3% and treatment ORR of 30% (alternative hypothesis) at a 0.05 significance level (i.e., alpha) using a one-sided Fisher's exact test. Power calculations were performed using nQuery Advisor 7.0. For both the NSCLC and uveal melanoma cohorts, an initial cohort of 3 patients will be followed for toxicity through the first cycle of nivolumab. If only 1 of 3 patients experience toxicity, then 3 more patients will be enrolled. If no more than 1 of 6 patients experience toxicity, then the trial will be fully opened. The staggering interval will be 5 weeks for the run-in cohort. Toxicity will be defined as any Grade 3 or greater toxicity excluding alopecia and constitutional symptoms as assessed by NCI CTCAE v4.03. Hematological toxicities will have a window of 21 days to resolve.

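### A RECIST 1.1 response can count toward the primary ORR from a single scan, the criterion that feeds the test is not named, and one unconfirmed response can decide a cohort

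*Combined protocol and SAP*

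**What the plan says.** Section 4 (Endpoints) and section 12.1 make ORR the primary endpoint and name RECIST 1.1 and modified irRC together as the response criteria. Section 15.1 gives the hypotheses and power for each cohort but does not say which criterion supplies the responder count.

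Section 12.2 defines a RECIST response by size alone. A PR is a fall of at least 30% in the sum of target-lesion diameters, "using the baseline sum diameters as the reference". It asks for neither a second scan nor a minimum duration. Section 12.3 then presents confirmation as a point of difference between the two systems: "In contrast to RECIST 1.1, the modified irRC criteria (a) require confirmation of both progression and response by imaging". Its interval is 8 weeks. Appendix D also requires confirmation of irCR and irPR, but at least 4 weeks apart and normally 6.

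Section 15.1 tests NSCLC with a "null hypothesis of ORR of 3% and treatment ORR of 25% (alternative hypothesis" and states that "a sample size of 16 patients achieves 80.3% power". The uveal melanoma cohort has 9 patients, the same 3% null, a 30% alternative and 80.4% power. Both tests are one-sided at 0.05.

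The response rates cited in section 1.1 are not all defined alike:
- **Labelled confirmed:** the randomized squamous NSCLC trial, 20% against 9% ("The confirmed objective response rate (ORR) was significantly higher with nivolumab than with docetaxel"), and the single-arm squamous NSCLC trial, 15% ("The major efficacy outcome measure was confirmed ORR as measured by an independent review committee (IRC").
- **Labelled durable:** the 56-patient uveal melanoma analysis, 2 of 56 or 3.6% ("durable objective responses (PRs) and stable disease").
- **No such label:** 17% in the phase 1b NSCLC cohort, 1.4% CR plus 18% PR in non-squamous NSCLC, and 3 of 8 in the uveal melanoma case series.

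**The concern.** Every confirmed responder is also an unconfirmed responder, so omitting confirmation can only add responders. With no control arm, nothing in the design offsets the additions. Each cohort's verdict turns on two or three responses, so a shrinkage that crosses the 30% line once, through measurement error or a short-lived change, can be the one that reaches the cut-off.

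The same patient could also be a responder by RECIST and a non-responder by irRC. As the plan names no governing criterion, the choice between two results could be made after the data are seen.

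**Working it through.** **Inputs.** From section 15.1: n = 16, p0 = 3%, p1 = 25%, stated power 80.3%; and n = 9, p0 = 3%, p1 = 30%, stated power 80.4%; both one-sided at 0.05. From section 4: CT every 8 weeks.

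**Formula.** P(reject) = P(X ≥ r | n, p) = 1 − Σ(k = 0 to r−1) C(n,k) p^k (1−p)^(n−k).

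**1. Reproduce the plan's figures.** The plan states no cut-offs. They are the smallest r that keeps the error at a 3% rate at or below 0.05.

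| Cohort | Cut-off | Error at 3% | Power | Stated power | Error with one response fewer |
|---|---|---|---|---|---|
| NSCLC | 3 of 16 | 0.0113 | 0.8029 at 25% | 80.3% | 0.0818 |
| Uveal melanoma | 2 of 9 | 0.0282 | 0.8040 at 30% | 80.4% | 0.2398 |

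The stated powers are therefore one-sample exact binomial figures. A two-group Fisher test with 16 or 9 per group would give only 0.287 or 0.211.

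**2. How often one response decides.** The probability of finishing exactly one short at a true 3% rate is:
- NSCLC: C(16,2) × 0.03² × 0.97¹⁴ = 120 × 0.0009 × 0.6528 = 0.0705, or 7.1%.
- Uveal melanoma: 9 × 0.03 × 0.97⁸ = 0.27 × 0.7837 = 0.2116, or 21.2%.

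**3. If single-scan scoring raises the counted rate.** The documents give no figure for the rise, so 4% to 7% is an assumed range.

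| Counted null rate | NSCLC, P(X ≥ 3 of 16) | Uveal melanoma, P(X ≥ 2 of 9) |
|---|---|---|
| 3% | 0.011 | 0.028 |
| 4% | 0.024 | 0.048 |
| 5% | 0.043 | 0.071 |
| 6% | 0.067 | 0.098 |
| 7% | 0.097 | 0.127 |

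Solving P(reject) = 0.05 gives 5.3% (NSCLC) and 4.1% (uveal melanoma).

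**4. What confirmation does to power.** If 3%, 25% and 30% are confirmed rates, sample size, cut-offs, error and power do not change. If 25% and 30% are unconfirmed and a share f fails confirmation (assumed; not in the documents), power is P(X ≥ r | n, p1(1 − f)).

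| f | NSCLC | Uveal melanoma |
|---|---|---|
| 10% | 73.3% | 74.5% |
| 20% | 64.8% | 67.5% |
| 30% | 54.9% | 59.3% |

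**The case against.** The strongest reply is that the plan never says RECIST decides the primary test. If modified irRC governs, confirmation is already required and the problem goes away. This stands as far as it goes: single-scan counting is a permitted reading, not the only one. But leaving the choice open is part of the defect.

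A reader might go further in four ways, none of which the documents support.

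- **That the 3% null is on a confirmed or durable scale.** Section 15.1 gives no source or definition for it. The 3.6% in uveal melanoma is only the nearest cited figure, durable is not the same as confirmed, and no rate is cited for NSCLC after prior immunotherapy, which is the population enrolled.
- **That all the protocol's benchmarks are confirmed or durable.** Several carry neither label.
- **That one transient shrinkage can reject the null.** It cannot do so alone. It matters only when the cohort already stands one short.
- **That the 0.05 level fails.** For the endpoint as counted, error at 3% is 0.011 and 0.028. A breach needs an assumed rise, and at 4% both cohorts remain below 0.05.

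The number of chances to cross the threshold is also easily overestimated. A full treatment year gives (17 + 365)/56 = 6.8, so six or seven scheduled scans at most. Treatment ends at progression, and the median PFS values cited in section 1.1 (2.3 months for nivolumab in non-squamous NSCLC, 2.6 months in uveal melanoma) cover fewer than two 8-week intervals. Those populations differ from this one, but many patients would have few scans.

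Finally, duration of response is a secondary endpoint, so short-lived responses would be visible in the report. They would still count in the primary ORR if RECIST governs.

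**Conclusion.** The point holds as a weakness in the responder definition. Sections 12.2 and 12.3, read together, let a RECIST response count from one scan, and no section says whether RECIST or irRC feeds the primary test. The direction of the effect is certain: responders can only be added.

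Its size is not known from the documents. The figures that need no assumption about inflation are the cut-offs (3 of 16, 2 of 9) and the probability of being one short at a true 3% rate (7.1%, 21.2%). The error range of 0.024 to 0.097 (NSCLC) and 0.048 to 0.127 (uveal melanoma) rests on an assumed counted null rate of 4% to 7%. Uveal melanoma has the smaller margin, passing 0.05 about one percentage point above the null.

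A mismatch between the endpoint and the 3% null is possible but not demonstrated. This is an inexpensive improvement worth making before analysis, not a flaw that invalidates the design.

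**What to change.** First reconcile the irRC confirmation interval between section 12.3 and Appendix D, so that there is one interval to refer to. Then, in sections 12.2 and 15.1:

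1. Name the one criterion that supplies the responder count for the primary test.
2. Count a RECIST 1.1 CR or PR in the primary ORR only if it is met again on a later scheduled CT; otherwise treat the patient as a non-responder.
3. State how a response first seen on the last scan is classified, since scheduled imaging may end before a confirming scan.
4. Report the unconfirmed ORR as a sensitivity figure.
5. State that 3%, 25% and 30% refer to confirmed response, and give the source of the 3%.

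The cost is a few sentences. The 8-weekly CTs already supply most confirming scans. The reported ORR may be somewhat lower. Sample size, cut-offs and error are unchanged if the planning rates are confirmed rates. If 25% and 30% were meant as unconfirmed rates, the loss of power in step 4 of the working applies: to between 73% and 55% (NSCLC) and between 75% and 59% (uveal melanoma) if 10% to 30% of responses fail confirmation. The sponsor should then say whether that power is acceptable.
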